13. TMT A & B
14. Practice trial: Walking back and forth the corridor

15. Randomized Trial- each trial will be done 1 time (without hearing aid):

1. Single cognitive task sub1 - [Baseline] while sitting (serial subtraction of 1) + record with phone
2. Single cognitive task sub3 - [Baseline] while sitting (serial subtraction of 3) + record with phone
3. Single motor – [Baseline] Walking on the ground for 1 min a 10 m long corridor – recording with a stopwatch
4. Dual task cognitive sub1 (DT\_sub1) - serial subtraction of 1 + #3 - recorded with stopwatch + record with phone
5. Dual task cognitive sub3 (DT\_sub3) - serial subtraction of 3 + #3 - recorded with stopwatch + record with phone

Using REDCAP:

16. DEMOGRAPHIC questionnaire (descriptive)
17. ABC – In healthy young adults ask: “have you never had any concern regarding: balance?” – if yes- fill up the questionnaire. (descriptive)

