7. TAKE OFF HEARING AID
8. Wearing the APDM on both feet and pelvic where the ISPS
9. Balance testing: Standing feet attached with E/O, Standing feet attached with E/C, foam with E/O, foam with E/C for 30 sec. (descriptive)
10. 20 min: computerized cognitive battery
11. Randomized Trial of TUG (without hearing aid):
  1. TUG - 2 repetitions
  2. TUG DT\_sub3- 2 repetitions
12. HI- MOCA or MOCA

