### **Data analysis:**

Each variable was inspected for extreme outliers (i.e., data points that fell more than 4 standard deviations [SD] away from the mean) using summary statistics and box plots. An extreme outlier was excluded from the final analysis. Normality of the variables was determined based on skewness and kurtosis. Number that is greater than +1 or lower than -1 indicate a substantially skewed distribution. For kurtosis, if the number is greater than +1, the distribution is too peaked and less than -1 indicates a distribution that is too flat. If the distribution was found to deviate from normality, non-parametric statistical analysis was conducted.

Descriptive statistics described the study sample for age, sex, height, weight, race, current medication, education level, exercise level, DHI, ABC, history of falls, MoCA and HI- MoCA. To determine if the groups are similar with respect to background measures and demographics a comparison of the three groups Normal hearing, Mild BHL and > Moderate BHL (moderate, moderately-severe, severe and profound) was done using one-way analysis of variance (ANOVA) or non-parametric Kruskal-Wallis Test for continuous measures and Chi-square analyses for categorical measures (e.g., gender).

For Aim #1: Compare single task (=ST) gait parameters between individuals age and education-matched with Mild BHL, > Moderate BHL and controls with Normal hearing and Aim #3: Compare the effect of a cognitive task on gait parameters (=DT) between age and education-matched people with Mild BHL, > Moderate BHL and control with Normal hearing: For the primary outcome measure, gait speed and its variability, and secondary outcome measures (stride length, stride time and their variability) during the 1-min walk, a mixed model repeated measures (RM)- ANOVA was conducted with 1 within-factor (task) of 2 levels (ST and DT ['subtraction 3']) and 1 between factor (group) of 3 levels (Normal hearing, Mild BHL, Moderate BHL). When the distributions were found to deviate from normality the Kruskal-Wallis' test was conducted for a between-group comparison and the Wilcoxon signed-rank test for a within-group comparison. Since I had a significant difference with age, I adjusted for age the ANOVA comparison.

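### The randomised order of the step 15 tasks is left out of the Aim 1/3 model and the Aim 4 DTC comparison, which costs precision if performance drifts over the runs

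*Combined protocol and SAP*

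**What the plan says.** Step 15 lists five tasks: two seated subtraction tasks, a silent 1-minute walk (ST), and 1-minute walks while subtracting 1 (DT_sub1) or 3 (DT_sub3). Its heading is "Randomized Trial- each trial will be done 1 time (without hearing aid". I read this as random order. The document does not describe how the order was generated, whether it was balanced within hearing groups, or whether it was written down.

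Under Data analysis, the model for Aims 1 and 3 has "1 within-factor (task) of 2 levels (ST and DT ['subtraction 3']) and 1 between factor (group) of 3 levels". The only covariate is age: "Since I had a significant difference with age, I adjusted for age the ANOVA comparison". For Aim 4, DTC (not defined in the document; read here as dual-task cost) is compared between the groups by one-way ANOVA or Kruskal-Wallis and then correlated with cognitive scores. No order or period term appears in any of these analyses. The section is written in the past tense, so the analysis appears to have been carried out already.

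**The concern.** Step 15 is in effect a five-period within-person design. The group x task interaction of Aim 3, whose primary outcome is gait speed and its variability, and DTC in Aim 4 both depend on the contrast between the silent walk and the subtract-3 walk, with one run of each. A participant may do the silent walk first and the subtract-3 walk fifth, or the reverse. If performance changes over the runs through learning or fatigue, that change enters the person's DT minus ST difference. With one run per task it cannot be averaged out within the person. A 1-minute walk averages over many strides, but position in the sequence is constant throughout the run.

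The study therefore randomises a nuisance factor and then does not use it. At stake are the width of the interval around the interaction and, in small groups, how far the one reported estimate is moved by an accidental difference in order between groups.

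**Working it through.** The plan gives no figure to reproduce: no sample size, SD, power or order effect is stated.

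**Inputs from the document.** Five tasks, one run each, in random order (step 15); a model with task, group and age (Data analysis, Aims 1 and 3); significance at 0.05.

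**Assumed inputs.** Fully random order; a linear drift of b per position, in units of the SD of DT minus ST, from 0 to 0.3; 10, 20 or 30 per group.

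**1. Position gap.** Let D = position of DT_sub3 minus position of the silent walk. One position out of five has variance (25 − 1)/12 = 2, and two distinct positions have covariance −2/4 = −0.5. So E(D) = 0 and Var(D) = 2 + 2 + 2 × 0.5 = 5. Enumerating all 120 orders gives the same values, with the silent walk first in half of them.

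**2. Variance of DT minus ST.** The inflation is 1 + 5b². Power is for a pairwise comparison that would have 80% power with no drift.

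| b | Inflation | Pairwise power |
|---|---|---|
| 0 | 1.00 | 80% |
| 0.1 | 1 + 5 × 0.01 = 1.05 | 78.1% |
| 0.2 | 1 + 5 × 0.04 = 1.20 | 72.5% |
| 0.3 | 1 + 5 × 0.09 = 1.45 | 64.3% |

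**3. Chance imbalance between two groups.** The SD of the difference in mean D is √(2 × 5/n): 1.0 position at n = 10, 0.71 at n = 20 and 0.58 at n = 30. At b = 0.2 the estimate is typically shifted by 0.20, 0.14 or 0.12 SD of DT minus ST.

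**4. Effect of using the order.** The three-group test on DT minus ST (equivalent to the group x task test) was simulated without and with D as a covariate, 4,000 runs per cell. The group effect was set for roughly 80% power without drift.

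| n per group | b | Power without order | Power with order |
|---|---|---|---|
| 10 | 0 | 0.752 | 0.732 |
| 10 | 0.1 | 0.720 | 0.724 |
| 10 | 0.2 | 0.670 | 0.746 |
| 10 | 0.3 | 0.577 | 0.723 |
| 20 | 0 | 0.781 | 0.776 |
| 20 | 0.1 | 0.750 | 0.762 |
| 20 | 0.2 | 0.693 | 0.762 |
| 20 | 0.3 | 0.617 | 0.771 |
| 30 | 0 | 0.786 | 0.776 |
| 30 | 0.2 | 0.705 | 0.778 |
| 30 | 0.3 | 0.619 | 0.784 |

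Type I error was 0.042 to 0.055 without the order term and 0.044 to 0.054 with it.

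**5. Before/after factor or run position.** Of the 20 ordered pairs of positions, 8 are one apart, 6 two, 4 three and 2 four, so E|D| = (8 + 12 + 12 + 8)/20 = 2. A two-level factor (silent walk before or after DT_sub3) therefore explains 2² = 4 of the 5 units of Var(D), leaving an inflation of 1 + b²: 1%, 4% or 9% at b = 0.1, 0.2 or 0.3. Run position removes all of a linear drift.

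**The case against.** The strongest reply is that randomising the order is itself the standard protection, and the plan has it. That is correct. A reader might infer that ignoring order biases the comparison of hearing groups. The document does not support that: with random order the position gap averages zero in every group, the usual standard error already contains the variation due to order, and simulated type I error stays close to 0.05.

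A reader might also infer that practice was uneven and distorts the dual-task effect, because step 14 provides only "Practice trial: Walking back and forth the corridor". That does not follow either. The schedule is the same for everyone, so it adds neither noise nor group imbalance. Step 11 has also already given every participant two single-task TUGs ("TUG - 2 repetitions") and two TUGs with subtraction of 3 ("sub3- 2 repetitions"). A common practice effect could at most move the overall ST-DT difference, and an order term would not remove it.

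Two further objections stand in part. First, the size is assumed: the loss is slight at b = 0.1 or below, and b = 0.3 implies 4 × 0.3 = 1.2 SD of change from first to fifth run, which nothing in the document supports. Second, the document does not say that the order was kept. If it was not, the existing data cannot be re-analysed this way. Nor does it rule out balanced lists.

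None of this argues against using the order where it exists. Period adjustment is standard for a within-person design, and its cost when there is no drift is small.

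**Conclusion.** The point holds as one of precision and reporting, not validity. The Aim 1/3 model and the Aim 4 DTC comparison leave out a randomised factor that may carry variance in DT minus ST. The excess variance is 5%, 20% or 45% at assumed drifts of 0.1, 0.2 or 0.3 SD per position, and nil without drift. Adding the order takes simulated power from 0.69 to 0.76 at 20 per group with b = 0.2. With no drift it takes it from 0.75 to 0.73 at 10 per group. Chance imbalance in order between groups also goes uncorrected, which matters more if groups are small; the document is titled a pilot study but states no sample size.

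These figures rest on a linear drift equal in all groups, fully random order, and values of b and n that the document does not give.

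**What to change.** - State how the order of the five tasks was generated, whether it was balanced within hearing groups, and whether it was recorded.
- Where the order was recorded or can be recovered, add it to the Aim 1/3 model. Either use a between-subject factor (silent walk before or after DT_sub3) with its task x order term, or run position (1 to 5) in a linear mixed model. Adjust DTC in Aim 4 the same way. Kruskal-Wallis takes no covariate, so where that route is used the order-adjusted linear model can be shown beside it as a sensitivity analysis.
- For any further participants, record the order and draw it from lists balanced within hearing group.

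The analysis change costs about one degree of freedom and needs no new measurements, only the order itself. Its downside is a power loss of about 0.02 at 10 per group if there is no drift. Balanced lists need only be prepared before the visits.

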18. SSQ12
19. Each participant will receive \$20 for participation and sign up a form that received the gift card

### **Instructions:**

#### **TUG:**

Instructions: “On the word GO you will stand up, walk to the line on the floor, turn around and walk back to the chair and sit down. Walk at your regular pace.”

The time to complete the test will be recorded using a stopwatch.

#### **DT SUB 1 TUG:**

Instructions: “On the word GO you will stand up, walk to the line on the floor, turn around and walk back to the chair and sit down. Walk at your regular pace. While walking you need to subtract 1 from a number that I will tell you (between 20 -100)”

### **DT SUB 3 TUG:**

Instructions: “On the word GO you will stand up, walk to the line on the floor, turn around and walk back to the chair and sit down. Walk at your regular pace. While walking you need to subtract 3 from a number that I will tell you (between 20 -100)”

-----

In DT cognitive TUG individuals will be asked to complete the walk while performing a cognitive task (counting backward by threes from any number between 20 to 100). The cut off times using DT TUG to discriminate between fallers and non-fallers in elderly is >15 seconds with an overall correct prediction rate of 87%.

### **Gait:**

“Walk straight ahead at your comfortable speed until you see the mark on the floor and then turn and walk straight ahead to the opposite direction. Keep walking until I will tell you to stop. The total time for walking is 1 min. If you lose your balance do whatever feels safe to stay steady. One of the researchers is going to walk next to you to prevent any fall”.

### **Gait Serial Subtraction 1**

“Walk straight ahead at your comfortable speed while counting backwards out loud in jumps of 1 from a number that I will tell. Start from the next number. For example, if I say 557, you start: 556, 555 and so on. When you see the mark on the floor you turn and walk straight ahead to the opposite direction. Keep walking and counting until I will tell you to stop. The total time for walking is 1 min. If you lose your balance do whatever feels safe to stay steady. One of the researchers is going to walk next to you to prevent any fall”.

### **Gait Serial Subtraction 3**

“Walk straight ahead at your comfortable speed while counting backwards out loud in jumps of 1 from a number that I will tell. Start from the next number. For example, if I say 557, you start: 554, 551 and so on. When you see the mark on the floor you turn and walk straight ahead to the

opposite direction. Keep walking and counting until I will tell you to stop. The total time for walking is 1 min. If you lose your balance do whatever feels safe to stay steady. One of the researchers is going to walk next to you to prevent any fall”.

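### The participant script for the subtraction-3 walk states a step of 1, contradicting its own example and the only dual-task level in the primary-outcome model

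*Combined protocol and SAP*

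**What the plan says.** The Instructions section gives a spoken script for each walking condition. The script headed Gait Serial Subtraction 3 tells the participant to count back in "jumps of 1 from a number that I will tell. Start from the next number. For example, if I say 557, you start: 554"; its full example is "if I say 557, you start: 554, 551 and so on". The script headed Gait Serial Subtraction 1 states the same step of 1, with the example "if I say 557, you start: 556, 555 and so on".

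Step 15 of the procedure list treats the two as separate conditions. Item 4 is the walk with subtraction of 1. Item 5, the DT_sub3 walk, is described as "serial subtraction of 3 + #3 - recorded with stopwatch + record with phone", where #3 is the one-minute walk. Item 2 is the seated counterpart: "Single cognitive task sub3 - [Baseline] while sitting (serial subtraction of 3) + record with phone". For the whole block, "each trial will be done 1 time (without hearing aid").

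Data analysis covers Aims 1 and 3 with one repeated-measures ANOVA for gait speed and its variability (primary) and the stride measures (secondary). Group has three levels. Task has two: single task, and dual task with subtraction 3. The subtraction-1 walk is not a level in that model.

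**The concern.** The text scripted for delivery defines the task. The stated step is what separates the DT_sub1 walk from the DT_sub3 walk, and here both scripts state the same step. A participant who followed the stated step rather than the example would do a serial-1 walk that is then analysed as serial 3.

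What could be affected:

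- **Primary model.** The task effect and the group-by-task interaction use the subtraction-3 walk directly. The group main effect averages over both tasks, so it is exposed too.
- **Non-parametric fallback.** The Wilcoxon comparison of single with dual task would be affected. A Kruskal-Wallis test on single-task gait alone would not, but the plan does not say that such a test is run.
- **Aims 2 and 4.** The dual-task cognitive score and the DTC could be affected where they use this walk. The document does not define DTC, so this is conditional.

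Two design features add to the exposure. Each walk is done once, so a wrong-step trial has no repeat. The script is also heard with hearing aids off (step 7, "TAKE OFF HEARING AID", and step 15) in a study whose groups are defined by hearing, so an equal rate of wrong-step counting across groups cannot be assumed. The documents neither show nor exclude a difference.

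**Working it through.** **1. Step implied by each example.**

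| Script | Stated step | Example | Step in the example |
|---|---|---|---|
| Gait Serial Subtraction 1 | 1 | 557 → 556, 555 | 557 − 556 = 1; 556 − 555 = 1 |
| Gait Serial Subtraction 3 | 1 | 557 → 554, 551 | 557 − 554 = 3; 554 − 551 = 3 |

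The first script agrees with itself; the second does not.

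**2. Can the wording about starting from the next number reconcile them?** Starting at 556, steps of 1 give 556, 555 and steps of 3 give 556, 553. Neither is 554, 551. Only a step of 3 applied to 557 reproduces the example.

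**3. Which value is the odd one out?** Four places say 3: the script's heading, its example, step 15 item 5, and the task factor in Data analysis. One says 1: the stated step.

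**4. Likely origin.** Compared word by word, the two scripts have 105 words each and differ in 2 (556 against 554, and 555 against 551). That fits a copy of the subtraction-1 script in which the example was edited and the step was not. This is an inference. The sentence is intact, so it is not a fault of text extraction.

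**5. How an error would enter the model.** Let x be the shift in one group's dual-task mean caused by wrong-step counting. With 2 task levels, 3 groups weighted equally, and no age adjustment:

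- that group's mean over tasks is (ST + DT + x)/2, a shift of x/2;
- its single-minus-dual contrast is ST − (DT + x), a shift of −x, which goes into the interaction;
- the task effect is the average of three such contrasts, a shift of −x/3.

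If all three groups shifted by the same x, every group mean would move by x/2, so group differences and the interaction would not change, and the task effect would move by −x.

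These weights hold for any design of this shape. x depends on the share of walks done with the wrong step and on the gait difference between serial 1 and serial 3. The documents give neither, so no size is estimated.

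**The case against.** The strongest reply is that this is a one-digit slip that probably never reached the data:

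- The correct example follows the wrong digit almost at once.
- Participants have already done the Timed Up and Go with subtraction of 3 (step 11, "sub3- 2 repetitions"), and the DT SUB 3 TUG script states the step correctly.
- The same randomized block contains a seated serial-3 task, although the random order need not place it before the walk.
- Counting is aloud with a researcher walking alongside, so a wrong step could be noticed at the time. Two identical walking conditions would also be likely to attract attention.
- Phone recordings exist, so scoring may expose a count by ones.
- Nothing shows that the written wording was what participants heard.

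All of this stands, and it lowers the likelihood of an effect. It does not remove the contradiction or settle which wording was used.

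Two narrower points are also fair. The argument about hearing groups is a possibility only, since mishearing could affect a correct script as well. And single-task gait, which is how Aim 1 is worded, is untouched in itself; Aim 1 is exposed only if the group main effect of the joint model serves as its test, which is a reasonable reading but is not stated.

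**Conclusion.** The concern holds. The stated step of 1 in the subtraction-3 script is wrong as written, and confidence in that is high because it follows from the document alone.

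The effect on results is unknown and may be zero. Any effect depends on the script having been delivered as written, on some participants having followed the stated step rather than the example, and on gait differing between the two counting tasks. The documents establish none of these.

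The point still deserves action rather than a note, because the slip sits in the only dual-task condition of the primary-outcome model and can be checked from material already collected. Sample size, significance level and the primary analysis are unaffected.

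**What to change.** 1. In the Gait Serial Subtraction 3 script, change the stated step from 1 to 3.
2. Data analysis is written in the past tense, so for sessions already run, state which wording was delivered.
3. Use the phone recordings of the DT_sub3 walk (step 15 item 5) to identify the step each participant used, and report the number of wrong-step walks by hearing group.
4. Only if wrong-step walks are found: keep all trials in the primary model, add one sensitivity analysis without them, and report how many participants leave the paired model in each group.

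The cost is a one-digit correction and a review of one recording of a 1-minute walk per participant. If the sensitivity analysis is needed, removing a DT_sub3 trial from a two-level repeated-measures ANOVA normally removes that participant. This may select on cognitive performance or hearing group and should be reported as a limitation.

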### **Data analysis:**

Each variable was inspected for extreme outliers (i.e., data points that fell more than 4 standard deviations [SD] away from the mean) using summary statistics and box plots. An extreme outlier was excluded from the final analysis. Normality of the variables was determined based on skewness and kurtosis. Number that is greater than +1 or lower than -1 indicate a substantially skewed distribution. For kurtosis, if the number is greater than +1, the distribution is too peaked and less than -1 indicates a distribution that is too flat. If the distribution was found to deviate from normality, non-parametric statistical analysis was conducted.

Descriptive statistics described the study sample for age, sex, height, weight, race, current medication, education level, exercise level, DHI, ABC, history of falls, MoCA and HI- MoCA. To determine if the groups are similar with respect to background measures and demographics a comparison of the three groups Normal hearing, Mild BHL and > Moderate BHL (moderate, moderately-severe, severe and profound) was done using one-way analysis of variance (ANOVA) or non-parametric Kruskal-Wallis Test for continuous measures and Chi-square analyses for categorical measures (e.g., gender).

For Aim #1: Compare single task (=ST) gait parameters between individuals age and education-matched with Mild BHL, > Moderate BHL and controls with Normal hearing and Aim #3: Compare the effect of a cognitive task on gait parameters (=DT) between age and education-matched people with Mild BHL, > Moderate BHL and control with Normal hearing: For the primary outcome measure, gait speed and its variability, and secondary outcome measures (stride length, stride time and their variability) during the 1-min walk, a mixed model repeated measures (RM)- ANOVA was conducted with 1 within-factor (task) of 2 levels (ST and DT ['subtraction 3']) and 1 between factor (group) of 3 levels (Normal hearing, Mild BHL, Moderate BHL). When the distributions were found to deviate from normality the Kruskal-Wallis' test was conducted for a between-group comparison and the Wilcoxon signed-rank test for a within-group comparison. Since I had a significant difference with age, I adjusted for age the ANOVA comparison.

Partial Eta Square (PET) Effect Size was reported for each main effect and interaction (small effect, PET  $\geq 0.08$ ; middle effect, PET  $\geq 0.20$ ; and high effect, PET  $\geq 0.32$ ). P-values with a value of  $p < 0.05$  were considered statistically significant. Bonferroni corrections were applied to post hoc comparisons as applicable.

For Aim #2: Compare cognitive function (i.e., the Neurocognitive Index) between individuals age and education-matched with Mild BHL, > Moderate BHL and controls with Normal hearing. One way ANOVA (or non-parametric Kruskal-Wallis Test) was used to compare the Neurocognitive Index between the three groups. Moreover, one way ANOVA (or non-parametric Kruskal-Wallis Test) was used to compare the secondary outcome measures, i.e., Composite Memory, Verbal Memory, Visual Memory, EF, Cognitive Flexibility, Complex RT, Working Memory and Sustained Attention and the cognitive ST and DT performance. I used one-way ANOVA with the dependent variable, the cognitive domain (Neurocognitive Index or any of the secondary outcome measures), and group as independent variable. For the raw scores I used the ACNOVA to adjust for age since we had significant age difference and these results do not present an age-matched score. Cohen's d effect size was calculated per comparison and was defined 'small' effect size as  $d = 0.2$ , 'medium' effect size as  $d = 0.5$  and a 'large' effect size as  $d = 0.8$ .

For Aim #4: Explore whether cognitive performance (i.e., the Neurocognitive Index) is correlated with DTC per group. One way ANOVA (or non-parametric Kruskal-Wallis Test) was used to compare the DTC between the three groups. Correlations between the cognitive domains and DTC were assessed using Pearson's correlation (or its non-parametric equivalent Spearman's, if the distributions are found to deviate from normality) for continuous variables. Pearson's correlation for each comparison was defined as 'little to none' for  $r = 0-0.24$ , 'fair' for  $r = 0.25-0.49$ , 'moderate to good' for  $r = 0.50-0.74$  and 'good to excellent' for  $r = 0.75-1.00$ . SPSS version 27 IBM (NY, US) was used for all statistical analysis.

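### The 4-SD rule excludes values on size alone, with no error check, no stated reference set and no analysis that keeps them

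*Combined protocol and SAP*

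**What the plan says.** The Data analysis section opens with the outlier rule: "Each variable was inspected for extreme outliers", meaning "data points that fell more than 4 standard deviations [SD] away from the mean", using summary statistics and box plots. The consequence follows at once: "An extreme outlier was excluded from the final analysis".

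The normality screen, based on skewness and kurtosis beyond ±1, is described after the exclusion: "If the distribution was found to deviate from normality, non-parametric statistical analysis was conducted".

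The rule covers every variable, so it reaches the main endpoint of Aims 1 and 3: "For the primary outcome measure, gait speed and its variability". That endpoint is compared across "1 between factor (group) of 3 levels (Normal hearing, Mild BHL, Moderate BHL").

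The section does not say whether the mean and SD come from the pooled sample, each group or each task. It does not require evidence of measurement error and plans no analysis with the excluded values restored. The documents give no group sizes and no outcome means or SDs.

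**The concern.** Distance from the mean does not show that a value is wrong. Gait variability cannot fall below zero, so a long right tail is plausible, and a participant with hearing loss and very unsteady gait would lie in that tail. Such a value may be part of the group difference that Aims 1 and 3 look for. Deleting it because it is large can bias the comparison of group means.

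The unstated reference set adds a second problem, because the two readings behave differently. With a pooled mean and SD, the rule can act unevenly across groups. With a mean and SD per group, it may be unable to act at all in small groups, so that even a gross sensor error would survive it. A reader cannot tell which applies.

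**Working it through.** The plan states no figure that could be reproduced here. The threshold (4 SD), the action (exclusion) and the number of groups (3) come from the Data analysis section. Group sizes, means, spreads and shapes below are assumptions.

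**1. Per-group reading: can the rule fire?** The largest standardised deviation in a sample of n occurs when one value lies at distance d and the other n−1 are identical. Its deviation from the mean is d(n−1)/n and the SD (divisor n−1) is d/√n, so the ratio is (n−1)/√n.

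- n = 15: 14/√15 = 3.61
- n = 17: 16/√17 = 3.88
- n = 18: 17/√18 = 4.007
- n = 20: 19/√20 = 4.25

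With divisor n the bound is √(n−1), which is exactly 4.00 at n = 17 and so still not more than 4. On either definition the rule cannot fire at 17 or fewer and first can at 18.

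**2. Pooled reading: what is removed, and from whom?** The bound does not bind for three groups of 20: 59/√60 = 7.62. The rule was simulated with 20 per group and 20,000 to 40,000 studies per scenario. Parameters are listed in the order normal hearing, mild, moderate or worse. The difference is the mean of the most impaired group minus that of the normal-hearing group, averaged over all studies, including those where nothing is removed.

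| Assumed outcome | Studies with a removal | Removals from the most impaired group | Average shrinkage |
|---|---|---|---|
| Normal, equal SD | about 0.1% | no concentration | almost none |
| Log-normal, log-SD 0.5, no group difference | 24% | one third | no true difference to shrink |
| Log-normal, log means 0/0.1/0.3, log-SD 0.35 in all | 13% | about four fifths | 0.373 to 0.361 (3%) |
| Log-normal, log means 0/0.2/0.4, log-SD 0.5 in all | 26-27% | 71% | 6% |
| Log-normal, log means 0/0.1/0.3, log-SD 0.35/0.35/0.5 | 37% | only this group loses data in 98% of firing studies | 0.464 to 0.407 (12%) |
| As above, log-SD 0.35/0.35/0.6 | 52-53% | the same, in 99% | 0.551 to 0.448 (19%) |

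The percentages follow directly: (0.373−0.361)/0.373 = 3%; (0.464−0.407)/0.464 = 12%; (0.551−0.448)/0.551 = 19%.

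**3. Order of steps.** Exclusion is described before the skewness and kurtosis check. In the log-normal scenarios with a group difference, with the check made on pooled values, deletion turned a variable that failed the check into one that passed in 17-61% of the studies where the rule fired. The exclusion can therefore also switch the analysis from rank tests to ANOVA.

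**The case against.** Four points on the other side deserve weight.

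- **The cut-off is lenient.** With normal, equal-SD data it removes about 0.001 values per variable per study. This stands, and it limits the point to skewed or unequally spread outcomes.
- **Skewed variables go to rank tests, where one extreme value has little leverage.** This largely stands. In the unequal-spread scenarios, 73-84% of pooled datasets still fail the normality screen after exclusion. Kruskal-Wallis power falls only from 46% to 44% and from 39% to 35%; with equal log-SD 0.35 it stays at 64%. With no group difference, type I error stays at 5.0%. The rank route does not remove the problem, because exclusion comes first and can change which test is used.
- **The per-group limit may never apply.** The documents do not say that the rule is applied within groups, and the wording reads more naturally as pooled. Box plots were used as well. The bound is exact, but whether it matters here is unknown. The per-group and pooled problems are also alternatives and cannot both affect the same analysis.
- **This is a pilot study, and perhaps nothing was excluded.** That may be so, but the documents do not report it.

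A reader might infer that the pooled rule, by its nature, strips data almost only from the impaired group. The documents do not support this: they give no outcome distribution, and the share runs from one third with no group difference to 99% under assumed unequal spread. A reader might also take the shrinkage to be 29-32%. That figure arises only in the unequal-spread scenarios and only among studies where the rule fired. Those studies already have inflated differences (0.52-0.53 and 0.61, against true values of 0.466 and 0.553), so it is not the expected bias.

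**Conclusion.** The point holds in a limited form and is minor. As written, the rule excludes values on size alone, without an error criterion, a stated reference set or an analysis that keeps the values.

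Under pooled use with a right-skewed outcome, and an impaired group that is shifted or more variable, it biases the mean difference toward zero. The average size is about 3-6% with equal log-SD and 12-19% with larger spread in that group. These figures rest on assumed log-normal distributions and 20 per group. With normal, equal-SD data the effect is negligible, and the loss of power is small where rank tests are used.

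Under per-group use, the rule is inoperative at 17 or fewer per group. Without group sizes, it cannot be said that this occurs.

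**What to change.** Exclude a value only for a documented recording or sensor fault, judged blind to hearing group. Keep all other values in the primary analysis. State whether the mean and SD for the 4-SD rule are pooled, per group or per task. Report the 4-SD exclusion as a sensitivity analysis, with the number of values removed per group and variable. If no value was removed, one sentence saying so closes the point.

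Analysing variability outcomes on the log scale is optional, since the plan already sends skewed variables to rank tests.

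The cost is a change of wording, one rerun and slightly noisier estimates where genuine extremes are kept.
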